### B1. PURPOSE OF PROTOCOL

In this pilot study, we aim to assess feasibility of subject identification and data collection, including specimen processing, as well as the rate of enrollment for a future, larger randomized, placebo controlled trial of the effect of prophylactic antibiotics for all patients with advanced cirrhosis admitted to the hospital without an existing indication for new antibiotic use. Specifically, we will assess the incidence of infection after the time of enrollment and associated outcomes.

### B2. SIGNIFICANCE AND BACKGROUND FOR THE STUDY

Advanced chronic liver disease/cirrhosis creates a state of relative immune-compromise, and, indeed, infections are a key precipitant of clinical decline in patients with cirrhosis. Specifically, infections of any kind are a common cause of acute on chronic liver failure (ACLF) and complicate 20-40% of hospital admissions of patients with cirrhosis. Although other pathogens are also important, the vast majority of infections in patients with cirrhosis are of bacterial origin. In other high-risk hospitalized patient populations, early initiation of antibiotics has been shown to reduce the need for intensive care unit (ICU) admission and short-term mortality. Unfortunately, the presentation of infection in patients with cirrhosis is protean and may be subtle. Diagnosis may be delayed by the absence of classic signs of infection such as fever and absolute leukocytosis. Vital diagnostic studies, such as paracentesis or other culture (blood, urine, or sputum) may be delayed or may not yield results until days after presentation. Delaying antibiotics until such studies result is inadvisable in patients with infection; however, empiric administration of antibiotics to all patients with cirrhosis admitted to the hospital would result in waste and increased risk of antibiotic resistance, *Clostridium difficile* infection, and other adverse effects. Sub-groups of patients with cirrhosis are already known to benefit from empiric/prophylactic antibiotics including those with acute upper gastrointestinal hemorrhage and those with increased risk of spontaneous bacterial peritonitis. The risk of infection increases with more advanced cirrhosis, as marked by higher Model for End-stage Liver Disease – Sodium (MELD-Na).

There are also biomarkers of systemic infection that, although not specific, may be used to identify patients more likely to have an active infection and thus allow more targeted use of empiric antibiotics. Specifically, increase in serum C-reactive protein (CRP, >25 mg/L) and Procalcitonin (>0.5 ng/mL) are associated with acute bacterial infection.

These factors may permit identification of patients who would benefit from prophylactic/empiric antibiotics. There has not, however, been investigation of the effect of prophylactic antibiotics on hospitalized patients with advanced cirrhosis beyond the sub-populations described above.

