Each subject's medical record will be reviewed to determine the calculated baseline CLIF-C ACLF score (Chronic Liver Failure Consortium (CLIF-C) Acute on Chronic Liver Failure). This will be computed using data (laboratory and physical examination) collected as part of standard of care. These data points include:

- bilirubin,
- creatinine,
- INR,
- West Haven grade of encephalopathy,
- mean arterial pressure, and
- peripheral oxygen saturation (SpO2).

A peripheral or central venous blood sample will be taken after consent is obtained. Approximately thirty milliliters (2 tablespoons) of whole blood will be collected. We will measure serum procalcitonin and C-reactive protein for the research study and store remaining specimen for potential future testing.

Patients will be excluded if there is a clinical indication for new treatment with antibiotics, e.g. upper gastrointestinal hemorrhage or apparent infection. Standard of care treatment will never be delayed.

**Randomization:** Each subject will be randomized to receive antibiotic treatment (ceftriaxone) or placebo (normal saline). Randomization will be blinded to patients, study investigators, and study staff. Only the BIDMC Research pharmacist will know treatment assignment. Randomization will be stratified by the presence of either serum creatinine  $\geq$  2.0 mg/dL and/or diuretic-refractory ascites.

**Study Intervention:** The research pharmacy staff will provide antibiotic or placebo in the form of masked vials of intravenous solution. This will consist of either 1 gr ceftriaxone or an equal volume of normal saline (approximately 100 mL). This administration will begin as soon as possible after enrollment and will be repeated once daily. If a subject is prescribed an equivalent intravenous antibiotic during the hospitalization (i.e., ceftriaxone, piperacillin/tazobactam, or a carbapenem), the study-treatment (ceftriaxone/placebo) will be withheld on those days. If the clinically prescribed antibiotic is subsequently discontinued prior to discharge, the study-treatment/placebo may be resumed. Study treatment will be discontinued on study treatment day 7, or at the time of discharge or liver transplantation, if such events occur earlier than treatment day 7.

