## B. Statistical Considerations

**Sample Size Justification:** We estimate there will be a small prevalence of occult infection among patients who are believed to be eligible after initial screening is completed. Patients with identified infection at the time of enrollment will not be randomized and instead be treated as per standard of care at the discretion of the medical staff. We estimate there may be 5-10 such patients who are thus enrolled but not randomized.

We aim to randomize a total of 40 subjects, assigned to active intervention vs. placebo; hence as many as 50 may be screened / consented to determine eligibility. This is a pilot study intended to assess feasibility of patient identification, administration of required testing and enrollment processing, and the rate thereof. The magnitude of observed effect will permit sample size estimation for a larger, more definitive study which we hope to complete subsequently. It is unknown how many subjects will need to be screened to complete this planned enrollment. We will also obtain information on the dropout rate and/or rate of use of therapeutic antibiotics which may alter enrollment goals for a future study.

**Data Analysis:** As stated elsewhere, the proposed study is a pilot study, not intended to provide definitive results. However, there are multiple outcomes of interest that will be recorded in order to permit planning of a future study.

The primary outcome is incident bacterial infection identified after randomization

screening (as defined below).

Secondary outcomes include:

1. In-hospital mortality;
2. 30-day mortality;
3. Incident acute on chronic liver failure (ACLF) defined as two or more of:
  - Grade 3-4 hepatic encephalopathy,
  - Need for renal replacement therapy,
  - Need for mechanical ventilation,
  - Need for vasopressors, or mean arterial pressure (MAP) <60 mmHg, or decrement of >40 mmHg in systolic blood pressure after volume resuscitation.
4. Change in calculated CLIF-C ACLF score;
5. Length of stay (LOS) after randomization;
6. Intensive Care Unit (ICU) transfer after randomization;
7. C difficile infection (positive stool polymerase chain reaction (PCR) or toxin-assay in the setting of diarrhea);
8. Increment in MELD-Na  $\geq 3$  points between randomization and discharge;
9. Acute kidney injury (increase in creatinine  $\geq 0.3$  mg/dL in 48 hr or  $>50\%$  from baseline (within previous 3 months) occurring after randomization;
10. Variceal hemorrhage.

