For purposes of analysis, deidentified subject clinical data documenting the metrics above will be stored in a password protected file within the BIDMC network. Analysis will be conducted at BIDMC using R-studio software. There are no additional statistical consultants currently affiliated with this study. Descriptive statistics will include the incidence of the primary and secondary categorical outcomes in each arm with comparison via Chi-square test or Fisher's exact test for rare events. As noted elsewhere, we do not anticipate this study will provide sufficient statistical power to demonstrate statistically significant differences between groups, but we will need to have an idea of the magnitude of effect prior to planning such a study and hope to obtain this information here.

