#### ***Inclusion Criteria:***

- Age  $\geq 18$
- Cirrhosis, as defined by liver biopsy (completed as standard care) or a composite assessment of available results from imaging or elastography, prior records, and laboratory studies
- MELD-Na  $\geq 18$  (Model for End Stage Liver Disease-Sodium, incorporating components of serum sodium, bilirubin, International Normalized Ratio (INR), and creatinine

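### Baseline MELD-Na, the plan's own marker of infection risk, is not an adjustment covariate, and neither it nor the stratification factor enters the crude comparison meant to size the next trial

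*Combined protocol and SAP*

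**What the plan says.** - **Risk marker.** Section B2 states: "The risk of infection increases with more advanced cirrhosis, as marked by higher Model for End-stage Liver Disease" – Sodium. It gives no strength of association.
- **Availability.** The Inclusion Criteria (B3.C) set a MELD-Na floor of 18 and describe the score as "incorporating components of serum sodium, bilirubin, International Normalized Ratio (INR), and creatinine". Every randomised subject therefore has a baseline value.
- **Stratification.** The Randomization paragraph of B3.A uses one combined factor: creatinine at or above 2.0 mg/dL and/or diuretic-refractory ascites.
- **Analysis.** The Data Analysis text in B3.B plans to report "the incidence of the primary and secondary categorical outcomes in each arm with comparison via Chi-square test", or Fisher's exact test for rare events. It names no model, stratified test or adjusted estimate. The covariate list (procalcitonin, C-reactive protein, other antibiotic use, fungal infection or antifungal use) omits baseline MELD-Na, and no analysis is tied to the list.
- **MELD-Na as an outcome.** A rise of 3 points or more between randomisation and discharge is secondary outcome 8.
- **Use of the result.** Under Sample Size Justification: "The magnitude of observed effect will permit sample size estimation for a larger, more definitive study". The same section disclaims definitive results, and the Data Analysis text disclaims power.

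**The concern.** The primary outcome is incident bacterial infection. The plan names one baseline score as a marker of infection risk and collects it in everyone, then leaves it out of the estimate of the effect on infection. The randomisation stratum is left out as well.

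With about 20 patients per arm, a visible difference in baseline MELD-Na between arms is quite possible. The investigators would then hold a single dataset with a known imbalance and no planned analysis that responds to it. An adjustment chosen after seeing the imbalance would be data-driven. What is at stake is the effect estimate carried into the next trial's sample size, not a significance test.

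**Working it through.** **Inputs from the documents.** "We aim to randomize a total of 40 subjects, assigned to active intervention vs. placebo". The allocation ratio is not stated, so 1:1 (20 per arm) is assumed. Section B2 says infections complicate 20-40% of admissions. That includes infections already present at admission, so it is only a rough stand-in for the incident rate.

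**Inputs assumed.** Odds ratio for infection per SD of MELD-Na: 1.5, 2 or 3. Control risk: 20% or 30%. Correlation of the stratum with MELD-Na: 0.5. The documents give none of these.

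**The plan's own figure.** The plan says "We estimate there may be 5-10 such patients who are thus enrolled but not randomized" and "hence as many as 50 may be screened / consented to determine eligibility". 40 + 5 = 45 and 40 + 10 = 50, so the 50 is reproduced. The 40 has no alpha, power or target effect behind it, so no formula can reproduce it.

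**1. Chance of imbalance.** Without stratification, the SE of the standardised mean difference is sqrt(2/20) = 0.316.
- P(|d| > 0.5) = 2 × [1 − Φ(0.5/0.316)] = 11%
- P(|d| > 0.3) = 34%

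Stratification shrinks the SE to sqrt((2/20)(1 − r²)), where r is the correlation between MELD-Na and the two-level stratum. If the trait behind the stratum correlates 0.5 with MELD-Na and is split at its median, r = 0.5 × sqrt(2/π) = 0.40 and the SE is 0.290.
- P(|d| > 0.5) = 8.5%
- P(|d| > 0.3) = 30%

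If 0.5 is instead the correlation with the two-level stratum itself, the SE is 0.274 and the chances are 6.8% and 27%. At 0.7 they are 2.7% and 18%.

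**2. Effect of a 0.5 SD imbalance on the crude risk difference, with no treatment effect.** Take MELD-Na as normal with within-arm SD 1 and arm means +0.25 and −0.25. Average expit(a + b·x) over each arm, with b = ln(OR) and a set to give the stated overall risk. The differences, in percentage points, are:

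| Risk | OR 1.5 | OR 2 | OR 3 |
|---|---|---|---|
| 20% | 3.2 | 5.2 | 7.4 |
| 30% | 4.1 | 6.6 | 9.4 |

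At 40% risk the OR 3 figure is 10.6. For scale, halving a risk of 20-30% is a difference of 10-15 points.

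On the odds-ratio scale, OR^0.5 gives 1.22, 1.41 and 1.73. Those are conditional odds ratios. The marginal odds ratios that a two-by-two table estimates are about 1.22, 1.37-1.38 and 1.57-1.59.

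**3. Share of total uncertainty.** In simulation (20 per arm, no stratification, 30% risk), the SD of the risk difference due to MELD-Na imbalance is 2.6, 4.2 and 6.1 points at OR 1.5, 2 and 3. The total SD is 14.8, 14.6 and 14.7. The squared ratios are 3%, 8% and 17%. The mean simulated difference is about 0 under every scheme.

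**4. Effect of adjustment.** Simulation used n = 40 and a stratum correlated 0.5 with MELD-Na. The model was linear, with arm, stratum and continuous MELD-Na, and HC3 standard errors.

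| OR per SD | Variance, adjusted / crude |
|---|---|
| 3 | 0.87-0.91 |
| 2 | 0.97-0.99 |
| 1.5 | about 1.00 |
| 1 (not prognostic) | 1.03-1.04 |

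Type I error was 3.7-4.6%. Adjustment cut the shift from a 0.5 SD imbalance to about 1 point or less.

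**5. Effect on the interval.** At 30% in both arms, the crude 95% half-width is 1.96 × sqrt(2 × 0.3 × 0.7/20) = 28.4 points. Multiplying by sqrt(0.87) gives 26.5; multiplying by sqrt(1.04) gives 29.0.

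**The case against.** The strongest reply is that this is a feasibility pilot with a descriptive analysis and no claim to power. Chance imbalance under randomisation is already inside the crude standard error, and an interval of ±26 points serves sample-size planning hardly better than one of ±28. The strength of the MELD-Na association is also assumed. The B2 sentence is general background, not evidence about incident infection in screened patients with MELD-Na of at least 18, and that floor narrows the range. Most of this stands, and it limits the size of the point. It does not remove it, because the plan makes the observed effect a deliverable, and a pre-specified adjusted estimate deals with an imbalance in the one dataset that will exist.

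A reader might infer more than the documents support:
- **That MELD-Na is absent from the analysis.** It is not: a rise in it is secondary outcome 8. Only baseline MELD-Na as a covariate is missing.
- **That imbalance passes into the estimate unchecked.** The stratum includes creatinine, a component of the score, and refractory ascites, a mark of advanced disease. Some balance is obtained, although bilirubin, INR and sodium lie outside the rule.
- **That the crude estimate is biased.** Over repeated randomisations it is not.
- **That MELD-Na should become a stratification factor.** In 40 patients a further stratum is not clearly better, and adjustment does not need it.

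**Conclusion.** The point holds as a minor gap in the analysis plan. Baseline MELD-Na is named as a risk marker and known for everyone, but neither it nor the stratification factor enters the comparison whose result is to size the next trial.

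Its size is modest. A 0.5 SD imbalance has a chance of about 8-9% under the 0.5 correlation, lower if the stratum tracks MELD-Na more closely, and at most 11%. When it occurs, it moves the crude risk difference by about 3 to 10 points. Averaged over all randomisations, adjustment reduces variance by about 13% at best, does nothing at an odds ratio of 1.5, and costs 3-4% if MELD-Na is not prognostic here. Sampling noise from 40 patients remains far larger.

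All of this rests on 1:1 allocation and on the assumed control risks, odds ratios and correlation. The omission itself rests on the text alone.

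**What to change.** Keep the crude incidences and the planned tests. Add to the Data Analysis text:
1. A table of baseline MELD-Na by arm.
2. A supportive adjusted risk difference for incident infection with 95% CI, from a model with arm, randomisation stratum and continuous baseline MELD-Na (the value at entry, not dichotomised). Choose the method before unblinding: a linear model with HC3 standard errors, or Firth logistic regression with standardisation to the risk-difference scale.

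Limit adjustment to these two terms. At 20-40% with no treatment effect, only 40 × 0.2 = 8 to 40 × 0.4 = 16 infections are expected, and fewer if the drug works.

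The cost is a sentence or two and a few lines of R, with no new data, patients or strata. The downside is a 3-4% larger variance for the supportive estimate if MELD-Na proves not to be prognostic.

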**B3. DESCRIPTION OF RESEARCH PROTOCOL****A. Study Design – Overview, Methods, Procedures**

This is a blinded, randomized, placebo-controlled pilot trial to determine feasibility of subject identification, rate of enrollment, and data collection, including specimen processing, for a future, larger randomized trial of the effect of empiric antibiotics for all patients with advanced cirrhosis admitted to the hospital without an existing indication for new antibiotic use. Specifically, we will assess the incidence of infection after the time of enrollment and associated outcomes. Patients will be randomized to receive either ceftriaxone or placebo (normal saline). Study drug will be delivered in masked vials for daily IV administration.

**Case finding and Screening:** Eligible patients will be identified in the emergency department or by admitting physicians upon their initial medical assessment or by study personnel via daily review of the inpatient hepatology ward and consultative service census. Study personnel will screen each potential subject by review of medical record for potential eligibility.

**Consent:** If a patient meets basic eligibility criteria, a study investigator will meet with the potential subject/LAR to review the study protocol and obtain informed consent. Screening measures will be completed following consent and the balance of the baseline measures will be completed.

**Extended Screening/Baseline:** Evaluation for undiagnosed infection will be completed following consent and prior to randomization including: chest x-ray, venous blood culture, urine culture- all, if not already performed via routine care. These studies may be deferred if they have been done within 7 days of enrollment and there has been no change in clinical status. Subjects with infection identified upon enrollment will be excluded from further participation and have further treatment directed by their standard clinical providers.

Each subject's medical record will be reviewed to determine the presence or absence of diuretic-resistant ascites (defined by history of TIPS, large volume paracentesis within the past 3 months despite diuretics, or intolerance of diuretics).

Each subject's medical record will be reviewed to determine the calculated baseline CLIF-C ACLF score (Chronic Liver Failure Consortium (CLIF-C) Acute on Chronic Liver Failure). This will be computed using data (laboratory and physical examination) collected as part of standard of care. These data points include:

- bilirubin,
- creatinine,
- INR,
- West Haven grade of encephalopathy,
- mean arterial pressure, and
- peripheral oxygen saturation (SpO2).

A peripheral or central venous blood sample will be taken after consent is obtained. Approximately thirty milliliters (2 tablespoons) of whole blood will be collected. We will measure serum procalcitonin and C-reactive protein for the research study and store remaining specimen for potential future testing.

Patients will be excluded if there is a clinical indication for new treatment with antibiotics, e.g. upper gastrointestinal hemorrhage or apparent infection. Standard of care treatment will never be delayed.

**Randomization:** Each subject will be randomized to receive antibiotic treatment (ceftriaxone) or placebo (normal saline). Randomization will be blinded to patients, study investigators, and study staff. Only the BIDMC Research pharmacist will know treatment assignment. Randomization will be stratified by the presence of either serum creatinine  $\geq$  2.0 mg/dL and/or diuretic-refractory ascites.

**Study Intervention:** The research pharmacy staff will provide antibiotic or placebo in the form of masked vials of intravenous solution. This will consist of either 1 gr ceftriaxone or an equal volume of normal saline (approximately 100 mL). This administration will begin as soon as possible after enrollment and will be repeated once daily. If a subject is prescribed an equivalent intravenous antibiotic during the hospitalization (i.e., ceftriaxone, piperacillin/tazobactam, or a carbapenem), the study-treatment (ceftriaxone/placebo) will be withheld on those days. If the clinically prescribed antibiotic is subsequently discontinued prior to discharge, the study-treatment/placebo may be resumed. Study treatment will be discontinued on study treatment day 7, or at the time of discharge or liver transplantation, if such events occur earlier than treatment day 7.

**Monitoring during Study Intervention:** Monitoring during study treatment will utilize routine vital sign monitoring and standard care labs conducted as indicated (typically daily) during the patient's in patient stay. Standard care monitoring may also include radiographic or microbiology studies (e.g. culture) or special procedures such as therapeutic or diagnostic paracentesis at the discretion of the inpatient care team. No additional monitoring will be required per the study protocol. Standard care monitoring/labs that will be of interests include vital signs (e.g. blood pressure, mean arterial pressure, and oxygen saturation), CBC with WBC differential, bilirubin, INR, serum creatinine, sodium, albumin.

**Incidental Findings:** In the event that a clinically significant incidental finding is discovered during a research procedure, findings will be immediately reported to the attending on service for treatment or referral; results will be in OMR. These would be also be available to the in-patients care team via OMR. Examples of incidental findings include previously un-identified lung findings on chest x-ray, such as infection, pulmonary nodule, fracture, etc.

**Safety Monitoring:** The PI is ultimately responsible for protecting the rights, safety, and welfare of subjects enrolled into the trial. Study intervention will last for 7 days during the patient's inpatient stay for conditions related to the diagnosis of advanced cirrhosis/end stage liver disease. Safety monitoring will be conducted daily during the intervention phase; post-intervention procedures will continue daily during the patient's admission and on day 30 post end of intervention. The PI and/or a co-physician investigator will review all safety parameters including clinical safety laboratory assessments. Clinical laboratory values that fall outside of the pre-specified safety ranges will be brought to the PIs attention the day the reports are final to assess clinical significance.

Patients in the trial will be under the care of the in-patient liver service and these medical staff will be responsible for care of the patient throughout the admission.

The study PI will review data of all non-serious adverse events after randomization of the first 5 subjects, and every additional 10 subjects thereafter until the study is complete.

**Monitoring for AE:** Subjects will be monitored for the occurrence of adverse events during their participation in the study. Reporting procedures will comply with BIDMC IRB policies; US Federal Regulations (21CFR 312), and ICH Guideline E-6: *Guidelines for Good Clinical Practice*.

Adverse events will be coded and graded according to the NIH/NCI Common Terminology Criteria for Adverse Events version 4.03 (June 2010). All adverse events will be classified on seriousness (mild, moderate, serious), expectedness (expected, non-expected), and relatedness to trial (not related, possibly related, related).

**End of treatment:** The study intervention will continue for 7 consecutive days (unless interrupted by equivalent antibiotic treatment for a new clinical indication). If the study intervention is interrupted the study intervention may be restarted following completion of the open label antibiotic treatment to complete the 7 days of study intervention.

**Follow-up Procedures:** Monitoring will continue until 30 days post-intervention.

**End of study:** Subject data will be recorded for up to 30 days post-intervention.

**Data/Tissue Repository:** A data and bio-specimen repository will be created to permit future research on this topic. De-identified data for each subject will be stored in a restricted access, password-protected folder on the BIDMC network drive. This access will be limited to study personnel. A master-code which links patient medical record number to the coded study subject ID will be stored in a separate location and available only to the PI and study personnel, as required for data entry. A blood specimen will also be collected from each subject upon enrollment for storage such that additional testing may be completed if preliminary results or subsequent knowledge suggest that another biomarker might have added prognostic significance. These specimens will be stored in a locked unit in the Liver Research Center (LMOB4) and coded with study ID only. Further testing on these specimens will not become part of the medical record.

